7.1 Screening procedures

The full details of history, physical examination, anthropometric measurements, 24-hours diet recall, physical activity of the patients will be recorded as per the proforma. OGTT is the critical investigation for this study and based on this the screening will be done. Investigations - HbA1c and Fasting blood sugar, Lipid profile, Liver function test, Renal function test, Electrolytes and Urine analysis will be taken before and after treatment and the reports will be recorded.

7.2 Follow-up Procedure

A prospective observation will be done for a period of one month after completion of the trial (6 months) by both groups. The drug intervention will be withdrawn in the drug group and LSM group will be on normal life style to measure the efficacy of the trial drug and LSM in both the groups. A comparison (physical assessment and blood sugar (OGTT) between the trial and non-trial period will be drawn in the outcome.

8. Safety and Efficacy Assessments

Liver function test and renal function test are recorded before and after trial drug administration to measure the safety of the drug. OGTT, HbA1c and blood glucose levels also measured for efficacy of the drug. Lipid profile is tested to measure the complementary benefit of the drug in microvascular end arterial diseases.

9. Adverse Event Reporting

If any adverse drug reaction or adverse event is reported, the study subject will be referred to the Pharmacovigilance cell of the study centre. According to the advice of the Pharmacovigilance cell withdrawal or continuation of the study will be determined.

10. Statistical Methods/Data Analysis

All the data will be entered in the Microsoft excel and the data will be analyzed using SPSS Version 16. Quantitative data shall be given in mean and standard deviation. Prevalence

shall be given in proportion with 95% confidence interval. Association with risk factors shall be analyzed using chi square test and multivariate analysis. Correlation shall be analyzed using Karl Pearson, with significant level ($P < 0.005$ or $P < 0.05$). Comparison between means with Annovatest, difference between means assessed by paired t test. Further analysis will be extended depending upon the results at the end of the study.

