5.1 Criteria for Exclusion:

Subjects with age below 30 and above 60 years are excluded in the study. The subjects are excluded in the study those who are known Diabetes, Malignant and accelerated hypertensive, Chronic Liver and Renal diseases, Coronary artery disease, Secondary Diabetes mellitus, CNS disorder (e.g. encephalopathy) and patient undergoing regular treatment for any other severe illness. Pregnant woman and planning to be pregnant within six months and lactating mother are excluded.

6. Study Drug:

The intervention group receives either trial drug or life style modification. The trial drug is an official Siddha formulation mentioned in Siddha Formulary. Recent animal studies have also proved its anti-diabetic activity. It is a kayakalpa drug having anti-oxidant potential, hypothetically assumed to act in IGT.

Dose: 500 mg Tablet , 4 tablets twice a day. Dose as per the market availability and the dose 4 gm / day is as per Marundhu Alavu Attavanai mentioned in Gunapadam Thatthu Jeeva Vaguppu.

The LSM group will be advised to adopt life style modifications (balanced diet along with brisk walking not less than 150 min/week.) These interventions will be measured via LSM intervention compliance form.

Duration of the medication: 180 days. Duration is to measure the range of HbA1c.

6.1 Study drug Compliance/Adherence:

The container will be checked and the tablets will be counted by which compliance will be checked during each and every visit. It can also be assessed based on the drug compliance

form (Form IV A) for drug intervention group. The LSM group can be assessed based on the LSM intervention compliance form (Form IV B).

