10.2 Sample size determination

60 is the sample size as per the phase (Exploratory trial) of the clinical trial. 30 subjects will be enrolled in each group.

11. Criteria for Success of Treatment

Prevention or non-transformation of IGT to full blown diabetes which is measured by the primary end point will be considered as criteria stated above.

12. Trial Monitoring and Data Analyses

The progress of the trial will be monitored by the Guide. Data analysis will be done by the investigator.

13. Ethical Review

Institutional Ethical Committee (IEC) of participating centre is sought for clearance certificate before the project is initiated. Patient's information sheet and informed consent form will be submitted (Regional Language - Tamil) along with project proposal for approval by IEC. Both will be maintained in duplicate. Consent form will be given to the subject and will be enrolled with proper consent. One copy of Patient Information Sheet (PIS) will be given to the patient at the time of entry to the trial.

Reference:

1. Shukla s.s et al fundamental aspects and basic concepts of Siddha medicines. SYST-Re pharm 2011; 2:48-54.
3. American Diabetes Association. Diagnosis and classification of diabetes mellitus. *Diabetes Care*.2010; 33:S62–S69.
4. Unwin N et al, Impaired glucose tolerance and impaired fasting glycaemia: the current status on definition and intervention. *Diabet Med*. 2002; 19:708–723.
5. International Expert Committee. International Expert Committee report on the role of the A1C assay in the diagnosis of diabetes. *Diabetes Care*. 2009; 32:1327–1334.
6. Anjana RM et al, Prevalence of diabetes and prediabetes (impaired fasting glucose and/or impaired glucose tolerance) in urban and rural India: Phase I results of the Indian Council of medical research-India Diabetes (ICMR-INDIAB) study, 2011, *Diabetologia*, 54:3022-7.
7. Diagnosis, Prognosis, and Treatment of Impaired Glucose Tolerance and Impaired Fasting Glucose, McMaster University Evidence-based Practice Center, Hamilton, Ontario, Canada
<http://archive.ahrq.gov/downloads/pub/evidence/pdf/impglucose/impglucose.pdf>

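### The on/off comparison in Section 7.2 cannot measure efficacy: it is zero for a lasting benefit and for an inert drug alike, and should be relabelled as describing persistence

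*Protocol*

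**What the plan says.** Protocol Section 7.2 sets up the off-treatment month: "A prospective observation will be done for a period of one month after completion of the trial (6 months) by both groups". On what changes in that month it says: "The drug intervention will be withdrawn in the drug group and LSM group will be on normal life style". The purpose follows directly: "to measure the efficacy of the trial drug and LSM in both the groups". The comparison that is to serve this purpose is: "A comparison (physical assessment and blood sugar (OGTT) between the trial and non-trial period will be drawn in the outcome". The section does not describe the comparison as one of durability, carry-over or rebound. It does not say which direction of difference is favourable, and it names no test.

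Other passages bear on the point:
- Section 6 fixes treatment length ("Duration of the medication: 180 days"), so the on/off boundary is day 180 and the follow-up visit is day 210 (Form II, visit 8).
- Section 3 defines the arms as lifestyle modification plus drug against lifestyle modification alone.
- Section 10 lists, among general methods, "difference between means assessed by paired t test", without linking it to 7.2.
- Section 10.1.1 defines success by a composite of 2-hour OGTT, fasting glucose and HbA1c, reached during or after treatment. Section 8 names OGTT, HbA1c and glucose as efficacy measures.
- Section 11 gives the aim as "Prevention or non-transformation of IGT to full blown diabetes".

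**The concern.** The purpose and the contrast in 7.2 do not match. Comparing values on treatment with values after stopping asks whether glucose moves when treatment ends. Whether the drug lowered glucose relative to lifestyle modification alone is a different question. A drug that corrects glucose tolerance and keeps it corrected, which is what Section 11 hopes for, shows no movement; neither does a drug that never worked.

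The contrast is also made within each arm, so it loses the protection of randomisation. Anything else that changes at day 180, lifestyle above all, is mixed with the withdrawal of the drug. If the comparison were reported under its stated purpose, a null result or a rise could be given a meaning about efficacy that it does not carry.

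**Working it through.** **No plan figure to reproduce.** The only design number is 60 subjects, 30 per arm (Section 10.2), justified by trial phase. No SD, effect size or power is given. All OGTT values, SDs, effect sizes and correlations below are therefore assumptions.

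**Step 1: what the contrast estimates.** Let E be the fall in mean 2-hour OGTT that the drug has produced by day 180, f the fraction of it retained at day 210, and L the rise from lifestyle slackening after day 180. In the drug arm:

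day 210 − day 180 = (1 − f)·E + L

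With L = 0 this is 0 if f = 1 (lasting benefit), 0 if E = 0 (inert drug), and E, its maximum, if f = 0 (purely transient). With E = 0 and L > 0 it is L, with no drug effect at all.

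**Step 2: illustrative means (mg/dl).** The test is approximated by a normal paired test with n = 30 and two-sided alpha 0.05. The assumed SD of the within-person difference is 15 to 30, so SE = SD/√30.

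| Profile | Day 0 / 180 / 210 | 7.2 contrast | Fall, day 0 to 180 | P(7.2 contrast significant), SD 15 to 30 |
|---|---|---|---|---|
| Lasting benefit | 170/135/135 | 0 | 35 | 0.05 |
| No effect | 170/170/170 | 0 | 0 | 0.05 |
| Partial rebound | 170/135/150 | 15 | 35 | >0.99 to 0.78 |
| Purely transient | 170/135/170 | 35 | 35 | about 1.00 |

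Example: with SD 30, SE = 30/√30 = 5.48. A contrast of 15 gives 15/5.48 = 2.74, and the chance of exceeding 1.96 is Φ(2.74 − 1.96) = 0.78.

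The first two rows cannot be told apart by the 7.2 contrast, whichever direction is called favourable. If no change counts as good, an inert drug looks as good as a lasting one.

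**Step 3: simulation.** The model has a person effect plus independent visit error at days 0, 180 and 210, with within/between SD ratio r of 0.6 to 1.0. The correlation between visits is 1/(1 + r²), that is 0.74 to 0.50. There are 30 per arm, two-sided alpha is 0.05, and effects are in units of the total SD. The paired day 210 versus day 180 test in the drug arm is set against a day-210 comparison of arms adjusted for day 0 (ANCOVA).

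| Scenario | Paired on/off test, drug arm | Day-210 ANCOVA |
|---|---|---|
| Durable drug effect, 0.75 SD | 5% | 90–99% |
| Purely transient drug effect, 0.75 SD | 98–100% | 5% |
| Inert drug, both arms slacken, 0.3 SD | 35–59% | 5% |
| Inert drug, both arms slacken, 0.5 SD | 76–95% | 5% |
| Inert drug, only the LSM arm slackens, 0.3 SD | 5% | 26–39% |
| Inert drug, only the LSM arm slackens, 0.5 SD | 5% | 59–80% |

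In this model the day-180 arm comparison faces the same 0.75 SD shift whether the effect later lasts or vanishes. It therefore detects both at the 90–99% of the first row. Slackening after day 180 cannot affect it.

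The last two rows matter for the fix. Section 7.2 says that the LSM group returns to its normal lifestyle and that the drug is withdrawn in the other arm. It does not say what happens to lifestyle modification in the drug arm. Read literally, the arms differ in lifestyle during that month, and a day-210 arm difference can then arise from an inert drug, in the drug's favour.

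**The case against.** The strongest reply is that 7.2 is a follow-up procedure, not the trial's efficacy criterion. Under 10.1.1, a participant who meets the composite at day 180 and still meets it at day 210 is a success, so durable benefit is not counted as failure in the trial's result. This stands, and it limits the point to one supplementary comparison.

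Second, 7.2 gives no favourable direction. A reader might infer that the protocol rewards rebound and would report a lasting benefit as lack of efficacy. The documents do not support that; the section could equally be meant to check whether control holds off treatment. What survives is that the stated purpose is efficacy and that neither direction of reading delivers it.

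Third, the paired t test is not tied to 7.2. Section 10 also lists ANOVA, the trial period is not pinned to day 180, and a statistical analysis plan might name the test. This is fair, but Step 1 concerns the contrast itself and holds for any test of it.

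Fourth, a reader might infer that the comparison has uncontrolled false positives. The 35–59% and 76–95% rates need lifestyle to slacken in the drug arm, which 7.2 does not say. If only the LSM arm relaxes, the drug-arm rate under no effect is 5%. The confounding is possible, not established.

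Fifth, the rejection rates largely follow from the assumed effects. That is true of their size. The 5% for a durable effect does not depend on them, because the contrast is then exactly zero.

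**Conclusion.** The point holds for the 7.2 comparison. Its stated purpose is efficacy, and the contrast chosen gives the same answer, zero, for a fully lasting benefit and for an inert drug, and its largest value for a purely transient effect. That is algebra and needs no assumption beyond lifestyle staying constant; if lifestyle changes in the drug arm, the contrast is harder still to interpret.

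The illustrated sizes (5% for a durable effect, 98–100% for a transient one) rest on an assumed 0.75 SD effect, correlations of 0.50 to 0.74, a day 180 versus day 210 reading, and the paired t test as the likely tool. It would go too far to say that the trial measures efficacy only in this way: the composite in 10.1.1 and the Section 8 measures are separate and are not affected. The matter is worth correcting in the protocol because the correction is cheap, but it does not undermine the primary endpoint.

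**What to change.** 1. In 7.2, replace the efficacy purpose with: to describe persistence or loss of effect after stopping. State that the within-arm change from day 180 to day 210 is descriptive and is not evidence of efficacy in either direction.
2. Draw efficacy from between-arm comparisons at the end of treatment: the 10.1.1 composite, supported by 2-hour OGTT at day 180 adjusted for day-0 OGTT (ANCOVA).
3. Report the day-210 between-arm difference in OGTT, adjusted for day 0, as persistence of the drug effect only if lifestyle is handled alike in both arms during that month. If it is not, label that difference as confounded by lifestyle.
4. Reconcile what 7.2 says each arm does in that month with the arm definitions in Section 3. Which arrangement to adopt is for the investigators.

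The cost is protocol wording and one extra analysis on the follow-up OGTT that 7.2 already promises. The visit note on Form III lists laboratory tests only up to visit VII, so the day-210 OGTT needs to be reconciled there. The downside is that the on/off change can no longer be cited as evidence of efficacy.

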6.1.1 Withdrawal of subjects due to non-compliance/ adherence

The investigator shall withdraw the patients from both groups of the study if

- Fasting blood sugar rises > 126 mg. /dl, or 2 hours OGTT blood sugar level increases > 199 mg/dl and are not controllable within 90 days.
- Any serious complication develops which requires urgent treatment with any other drug / therapy.

The investigator will mention the probable cause of withdrawal and provide possible medical treatment to manage the illness. The patient will be withdrawn if the above said parameters shoot up in his blood picture due to non-compliance.

6.2 Study Drug Supplies:

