41. SGOT (IU/L) _____

- 42. SGPT (IU/L) _____
- 43. Alk. Phosphatase (KA units) _____
- 44. Total proteins (gm/dl) _____
- 45. Albumin (gm/dl) _____
- 46. Globulin (gm/dl) _____
- 47. A/G Ratio _____

Serum Electrolytes

- 48. Sodium (mEq/L) _____
- 49. Potassium (mEq/L) _____
- 50. Chloride (mEq/L) _____

Sl.No.10-50 will be done during I visit (0 day), IV visit (90th day) and VII visit (180th day).

Sl.No.28 & 29 (Blood Sugar- F & PP) in the following visits II, III, V and VI.

Date:

--	--

--	--

--	--

Signature of Investigator/ Medical Officer

**OPEN LABELED RANDOMIZED CONTROLLED CLINICAL TRIAL ON
IMPAIRED GLUCOSE TOLERANCE –IGT (Munneerizhivu)**

**FORM II - CLINICAL & PHYSIOLOGICAL ASSESSMENT
[Before Treatment & During monthly visit]**

1 st visit – 0 day		5 th visit – 120 th day	
2 nd visit – 30 th day		6 th visit – 150 th day	
3 rd visit – 60 th day		7 th visit – 180 th day	
4 th visit – 90 th day		8 th visit – 210 th day	

1. Code No. (Clinical trial)
2. Centre : Siddha Central Research Institute, Arumbakkam, Chennai.
3. Name of the Patient _____
4. S. No. of Patient _____
5. Gender Male (1) Female (2)
6. Date of Birth Age (Years)
7. Address _____

Chief complaint with duration (if any) in days (mostly asymptomatic)

- | | Absent (0) | Present (1) |
|------------------------------------|---|---|
| 8. Polyuria (Excessive Urine) |  |  |
| If present, duration in days _____ | | |
| 9. Polyphagia (Excessive Hunger) |  |  |
| If present, duration in days _____ | | |
| 10. Polydipsia(Excessive Thirst) |  |  |

If present, duration in days _____

11. Exhaustion/Tiredness

If present, duration in days _____

Absent (0)

Present (1)

12. Body ache

If present, duration in days _____

VITAL SIGNS

13. Pulse rate/min

14. Heart rate/min

15. BP(mm of Hg)

 /

16. Temperature °F

 .

PRESENT(1)

ABSENT (2)

17. Cyanosis

18. Anaemia

19. Jaundice

20. Clubbing

21. Lymphadenopathy

22. Oedema

23. Height/cm

 .

24. Weight/Kgs

 .

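### No liver or renal test is scheduled when a participant stops early, so someone withdrawn for harm before day 90 can have no post-dose result for the safety endpoint (10.1.2)

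*Protocol*

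**What the plan says.** Section 8 sets the intent: "Liver function test and renal function test are recorded before and after trial drug administration to measure the safety of the drug". Section 7.1 likewise places these tests before and after treatment. Neither gives a day, and neither says when the second test falls for someone who stops early.

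The days appear only in the footer of Form III: "Sl.No.10-50 will be done during I visit (0 day), IV visit (90th day) and VII visit (180th day"). Items 31-33 are the renal tests, 39-47 the liver tests and 48-50 the electrolytes, so all lie in this range. For the remaining visits of the treatment period the footer says: "Sl.No.28 & 29 (Blood Sugar- F & PP) in the following visits II, III, V and VI". By the visit list on Form II, those are days 30, 60, 120 and 150.

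Section 6.1.1 has two withdrawal triggers. One is glycaemic and applies to values that "are not controllable within 90 days". The other can occur at any time: "Any serious complication develops which requires urgent treatment with any other drug / therapy". What must then be done is also stated: "The investigator will mention the probable cause of withdrawal and provide possible medical treatment to manage the illness". Section 9 says: "If any adverse drug reaction or adverse event is reported, the study subject will be referred to the Pharmacovigilance cell of the study centre". The cell's advice then decides whether the participant continues. Section 7.2 adds a month of observation after the six-month trial, and its content is given as: "A comparison (physical assessment and blood sugar (OGTT) between the trial and non-trial period will be drawn in the outcome".

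Section 10.1.2 makes normal liver and renal tests the safety endpoint. It names no day.

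**The concern.** Liver and renal tests are the only safety endpoint that the protocol states, and they serve its only secondary objective, toxicological data (2.2). People taken off the drug for a complication or an adverse event are the ones whose liver and renal values would say most about harm. If staff follow the dated form, those who leave before day 90 contribute only a baseline value. The endpoint would then be read from people who tolerated the drug long enough to reach a scheduled panel, and it would lean towards a safe result.

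This is a matter of data collection. An analysis plan can decide how to treat a missing value, but it cannot supply blood that was not drawn.

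**Working it through.** The protocol has no figure of its own on this point to reproduce. The check has two parts.

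**1. What the schedule yields by time of stopping**

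| Stops | Scheduled liver and renal results | Position for 10.1.2 |
|---|---|---|
| Before day 90 | Day 0 | No post-dose result |
| Between days 90 and 180 | Days 0 and 90 | One on-treatment result, usable; none at or after stopping |
| Completes | Days 0, 90 and 180 | Complete |

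No other section fills the first row:
- Section 6.1.1 asks for the cause and for treatment. It withdraws the participant from the study, so a later day-180 visit cannot be assumed.
- Section 9 asks for referral and advice. It names no test.
- Section 7.2 begins after completion of six months and lists physical assessment and OGTT only.
- Forms II and IV B list visits up to day 210 but hold no liver or renal items.

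Glycaemic withdrawals mostly reach the day-90 panel because of the 90-day condition, so they belong largely to the second row. The first row consists mainly of withdrawals for a complication or an adverse event.

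**2. Illustration of size**

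Inputs: 30 participants per arm (section 10.2); k participants in the drug arm stop before day 90 for a complication or adverse event and go untested. The protocol gives no dropout rate, so k = 1 to 3 is an assumption.

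Formula: the one-sided 95% Clopper-Pearson upper bound for x abnormal out of n is the 0.95 quantile of Beta(x + 1, n − x). For x = 0 it equals 1 − 0.05^(1/n).

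| k | Observed if all tested are normal | Upper bound | Full result if all k were abnormal | Upper bound |
|---|---|---|---|---|
| 1 | 0/29 = 0% | 9.8% | 1/30 = 3.3% | 14.9% |
| 2 | 0/28 = 0% | 10.1% | 2/30 = 6.7% | 19.5% |
| 3 | 0/27 = 0% | 10.5% | 3/30 = 10.0% | 23.9% |

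If none of the k would have been abnormal, the full result is 0/30 with an upper bound of 9.5%. The only loss is then a bound of 9.8% to 10.5% in place of 9.5%.

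**The case against.** The best defence is that sections 7.1 and 8 already cover the case. They tie the second test to the end of treatment or drug administration, without limiting it to completers or to day 180. The Form III footer fixes days for planned visits and does not say that tests are taken on those days only. On that reading the point asks for operational detail. The intent is indeed clear, and this part stands. What is missing is anything that carries it out: no visit, form or withdrawal instruction tells staff to draw the sample at stopping, and the one dated instruction leads them not to.

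A second argument is that section 10.1.2 does not ask for a value after treatment. This stands in full. A reader might infer that everyone who stops early is lost to the safety endpoint, but the text does not support that. Those who stop after day 90 have an on-treatment result that can count.

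Third, a reader might infer that harm would go unnoticed. The text does not support this either: reported events go to the Pharmacovigilance cell, and the cause of withdrawal is recorded. The cell may also order tests. But nothing requires it to, and nothing says that such a result would enter 10.1.2.

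Fourth, the size rests on an assumed count, and its upper end needs three early stoppers, all untested and all abnormal. No test or decision threshold is attached to 10.1.2, and the trial is labelled exploratory. These limits hold and keep the point modest.

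**Conclusion.** The gap is real but narrow. It is complete only for participants withdrawn before day 90, chiefly for a serious complication or an adverse event; they have no scheduled post-dose liver or renal result. For withdrawals between days 90 and 180 it is partial, since the day-90 result remains.

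The number affected is unknown and probably small. Under the assumption of 1 to 3 such participants among 30, the effect on the observed abnormal rate runs from none to 0% shown where 10.0% was true. That is a range of possibilities, not an estimate of bias.

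The point merits a change because the missing values would fall on the people most likely to show harm, and because they cannot be recovered later. It does not show that the safety conclusion would be wrong.

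**What to change.** Add to sections 6.1.1 and 9: *For any participant in either arm who stops early, Form III items 31-33 and 39-50 (renal, liver and electrolytes) are taken at the stopping visit.*

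Add to section 10.1.2: *Any abnormal post-baseline result counts, whether from day 90, the stopping visit or day 180.* This also settles which result is used for those who stop after day 90.

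Cost: two short additions to the text and one extra routine blood draw for a few early stoppers. The draw is additional, because a withdrawn participant would not otherwise have had the day-180 panel. The safety result may look less favourable. Participants who do not return will still be untested, so the number without a post-baseline result should be reported by arm beside the endpoint.

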The investigational drug is a polyherbal Siddha formulation. It is proven as an anti-diabetic^{3, 4, 6}. Some studies have investigated the possible anti-diabetic properties of combination drug in animal models, one in a high fructose diet induced and another in alloxan diabetic rats^{3, 5}. The results of these studies show that the administration of the extracts reduced the blood sugar level. Gallic acid is the component present in the composition of investigational drug having anti-diabetic activity⁷. More over the same studies highlighted the anti-oxidant and anti-obesity effects of this drug. These effects are assumed to play a major role to reduce the chances of transition of IGT patients to established diabetics. According to ICMR-INDIAB study conducted

in 2011, 3.9 million are estimated to be in the state of prediabetes in Tamil Nadu. Projections for the whole of India would be 77.2 million pre-diabetic patients¹⁰. So a poly-herbal formulation which is more effective, cost effective and safety among prediabetes patients.

According to the above references life style modification is done holistically in this study with the study drug.

2. Clinical Study Objectives:

2.1 Primary objective:

To assess the efficacy of Siddha formulation in the individuals having Impaired Glucose Tolerance (IGT) – (Munneerizhivu). If, during treatment or after treatment OGTT 2 hours remain between 126 mg/dl and 140 mg/dl, fasting blood sugar between 70 mg/dl and 100 mg/dl and HbA1c is $\leq 6.0\%$ it will be treated as successful outcome of the treatment.

2.2 Secondary objective:

To determine the Toxicological data of Siddha formulation

[figure not shown]
3 Study Design:

Open labelled Randomized Controlled Clinical Trial.

There will be two arms in this study. To one group is assigned life style modification and test drug and to the other group Life Style Modification (LSM). Randomization will be achieved through Random numbers.

3.1 Allocation to treatment:

The subjects will be allocated to the drug interventional group and LSM group based on the Random numbers generated by the computer.

Schematic representation of Study Design

5 Criteria for Inclusion:

Subjects in their 3rd to 6th decade only will be included in this study. Subjects falling in any one of the following criteria i.e. 2 hours OGTT should be between 140 mg and 199 mg. Glycated hemoglobin (HbA1C) > 6.0% and <6.5% and Blood sugar – Fasting > 100 and =< 125 mg/dl will be included.

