8. The Diabetes prevention program (DPP) Research Group. *Diabetes care*, 2002, 25:2165-2171.

**OPEN LABELED RANDOMIZED CONTROLLED CLINICAL TRIAL ON
IMPAIRED GLUCOSE TOLERANCE –IGT (Munneerizhivu)**

FORM I - SCREENING PROFORMA

1. Code No (of clinical trial)
2. Centre: _____
3. Name of the Patient _____
4. S. No. of Patient _____
5. Gender Male (1) Female (2)
6. Date of Birth Age (Years)
7. Address _____

Mobile:

Phone no:

CRITERIA FOR INCLUSION

Yes (1)

No (0)

- | | | |
|---|----------------------|----------------------|
| 8. Age between 30 years and 60 years |  |  |
| 9. OGTT – After 2 hours < 140 mg and > 199 mg |  |  |
| 10. Glycated hemoglobin (HBA1C) >6.0% and <6.5% |  |  |

11. Blood sugar – Fasting > 100 and =< 125 mg/dl

CRITERIA FOR EXCLUSION

12. Age below 30 and above 60 years.

13. Malignant and accelerated hypertensive

14. CVS disorder (CAD)

15. Pregnant woman or the women planning to be pregnant in next six months

16. Lactating mothers

17. Secondary Diabetes mellitus

18. Patient undergoing regular treatment for Diabetes or for any other severe illness

19. CNS disorder e.g. encephalopathy

If yes to S.No.8-11 admit the patient into the study.

If admitted subject _____ No. _____

Date: _____

Signature of the Doctor _____

**OPEN LABELED RANDOMIZED CONTROLLED CLINICAL TRIAL ON
IMPAIRED GLUCOSE TOLERANCE –IGT (Munneerizhivu)**

FORM I A – SELECTION PROFORMA

1. Code No. (Clinical trial)
2. Centre :
3. Name of the Patient _____
4. S. No. of Patient _____
5. Gender Male (1) Female (2)
6. Date of Birth Age (Years)
7. Address _____

8. Educational status
Illiterate (1) Read & Write (2)
Educational qualifications _____ (3)
9. Occupation
Desk Work (1) Field Work (2) Others Specify _____
10. Income per capita per month in ₹ _____

Chief complaint with duration (if any) in days (mostly asymptomatic)

- | | Absent (0) | Present (1) |
|------------------------------------|----------------------|----------------------|
| 11. Polyuria (Excessive Urine) |  |  |
| If present, duration in days _____ | | |
| 12. Polyphagia (Excessive Hunger) |  |  |
| If present, duration in days _____ | | |
| 13. Polydipsia(Excessive Thirst) |  |  |
| If present, duration in days _____ | | |

Absent (0)

Present (1)

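### Section 10 gives its chi-square test to risk factors and its only 95% confidence interval to prevalence, and gives neither to the arm difference in the binary primary endpoint

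*Protocol*

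**What the plan says.** Section 10 (Statistical Methods/Data Analysis) summarises quantitative data by mean and standard deviation. It then says that prevalence "shall be given in proportion with 95% confidence interval", and next: "Association with risk factors shall be analyzed using chi square test and multivariate analysis". No risk factor is named, nor the outcome with which it is to be associated. Pearson correlation follows, "with significant level ($P < 0.005$ or $P < 0.05". Means are compared by analysis of variance and a paired t test, and further analysis may be added once the results are known.

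Sections 2.1 and 2.2 give two objectives, efficacy and toxicology. Section 10.1.1 defines the primary endpoint as a composite success on 2-hour OGTT, fasting glucose and HbA1c, which is a yes/no outcome.

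On who enters, Section 5 says "Subjects falling in any one of the following criteria i.e. 2 hours OGTT should be between 140 mg and 199 mg", with HbA1c and fasting limits ending "Blood sugar – Fasting > 100 and =< 125 mg/dl will be included". Form I is stricter: "If yes to S.No.8-11 admit the patient into the study", where three of the four items are glycaemic. On size, Section 10.2 says "60 is the sample size as per the phase (Exploratory trial) of the clinical trial" and "30 subjects will be enrolled in each group".

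**The concern.** Prevalence with a confidence interval, and risk-factor association by chi-square and multivariate analysis, are the tools of a population survey. This is a two-arm randomised trial in people already selected for the condition. The one categorical test and the one interval in the section are therefore attached to quantities that the trial does not set out to estimate, and the comparison that it does set out to make is left without them.

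Two things are at stake. A report that follows Section 10 could present a chance association between a baseline item and outcome as a finding. It could also show the drug effect only as a p-value on means, so that a non-significant result is read as no effect when the data are compatible with a large one.

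**Working it through.** **1. Can prevalence and risk factors for the condition be estimated?** Section 5 admits on any one glycaemic criterion, whereas Form I requires a yes to all its glycaemic items. The two rules differ, but under either the intent is that everyone enrolled has raised glycaemia. The baseline proportion with the condition is thus set by the entry rule. There is no unaffected group, so factors for having the condition cannot be estimated. This step needs no assumption.

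**2. What if association means predictors of success?** The protocol gives no number of factors and no success rate, so both are assumptions.

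- *Factors.* Form I A records about 14 candidates: age, sex, education, occupation, income, diet, anxiety, constipation, activity, smoking, tobacco, alcohol, constitution and BMI. The anthropometric form adds waist and waist-to-hip ratio, making 16. Range used: 12 to 16.
- *Successes.* Assumed 30-50% of 60, that is 18 to 30.
- *Events per factor.* From 18/16 = 1.1 to 30/12 = 2.5, very few for a multivariable model.
- *Chance of at least one false positive* with k independent null tests at level a is 1 − (1 − a)^k:

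| k | a = 0.05 | a = 0.005 |
|---|---|---|
| 12 | 1 − 0.95^12 = 46% | 1 − 0.995^12 = 5.8% |
| 16 | 1 − 0.95^16 = 56% | 1 − 0.995^16 = 7.7% |

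- *Power to detect a real predictor* (two-sided, n = 60, assumed success without v with the factor):

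| Success rates | 30/30 split, 0.05 | 15/45 split, 0.05 | 30/30 split, 0.005 |
|---|---|---|---|
| 30% v 50% | 0.35 | 0.26 | 0.11 |
| 20% v 40% | 0.39 | 0.27 | 0.13 |
| 30% v 60% | 0.65 | 0.52 | 0.31 |

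The stricter level controls chance findings but leaves little power.

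**3. What would an interval on the arm difference show?** Section 10.2 states no effect size, standard deviation, success rate or power, so the figure of 60 cannot be reproduced. The precision that 30 per arm gives can be.

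- *Success difference*, same rate p in both arms: half-width = 1.96 × √(2p(1 − p)/30).
  - p = 0.5: 1.96 × √(0.50/30) = 0.253
  - p = 0.3: 1.96 × √(0.42/30) = 0.232
  - p = 0.1: 1.96 × √(0.18/30) = 0.152
- *Difference in means*, unadjusted: t with 58 degrees of freedom × √(2/30) = 2.0017 × 0.2582 = 0.517 SD.

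For example, an observed success difference of 10 points at rates near 50% would carry an interval from about −15 to +35 points. A p-value alone would not show this.

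**The case against.** The strongest reply has four parts.

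- *An interval for a treatment difference is ordinary SAP content, and the SAP is not shown.* This stands as far as it goes. A reader might infer that the trial will report no precision for the drug effect, but the protocol does not exclude an interval, and its silence alone is no error. What remains is what Section 10 does state: it commits the chi-square test and the interval to other quantities.
- *Prevalence may loosely mean any proportion, including success in each arm.* That reading is possible, since the sentence follows the one on quantitative data. The proportion with diabetes or impaired tolerance at day 180 is also not fixed by entry, and Section 11 counts non-transformation to diabetes as success. Even so, the interval would be on a single proportion and not on the difference between arms.
- *Association with success can be computed, and the trial is exploratory.* This also stands. It would be too strong to say that 60 people cannot support any such analysis. They cannot support risk factors for the condition; for predictors of success the result is unreliable.
- *The false-positive figure depends on assumed inputs.* A reader might infer that the report will probably name a spurious factor. The documents do not support that. The 46-56% needs 12 to 16 independent factors, all tested at 0.05. Smoking and tobacco are likely to be correlated, fewer items might be tested, and at 0.005 the figure is 6-8%.

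Analysis of variance could also give a between-arm p-value on means, so the arms are not left wholly uncompared.

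**Conclusion.** The point holds as a misdirection of stated analyses. Section 10 names one categorical test and one interval, and assigns both to quantities outside the objectives, which for the condition itself cannot be estimated in a sample selected for it. No sentence assigns a test or an interval to the arm difference in the Section 10.1.1 endpoint. That much rests on the text alone.

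The size of the chance-finding risk rests on assumptions and runs from about 6% to 56%, depending on the level and the number of factors. The protocol fixes neither, and it allows further analysis chosen after the results. The precision figures rest on 30 per arm and assumed success rates. This warrants a wording change; it is not a defect of the design.

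**What to change.** Replace the prevalence and risk-factor sentences in Section 10 with:

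*The proportion meeting the primary endpoint will be compared between arms by chi-square (Fisher's exact test if expected counts are small), and the difference given with a 95% confidence interval. Between-arm differences in OGTT, fasting glucose and HbA1c, adjusted for the baseline value, will be given with 95% confidence intervals. Any association of baseline factors with success is descriptive, labelled exploratory, and supports no conclusion.*

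This keeps a named test for the binary endpoint and still allows predictor tables. It needs no new participants, visits or measurements. The small downside is that the predictor analysis is reduced to description.
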